Programming of the device is completed using the MAX Programming Interface and MAESTRO System Software. The MAESTRO software is used for different intraoperative and postoperative purposes for the MED-EL Cochlear Implant System. It contains the implant Telemetry, Fitting and Configuration of all available audio processors, ART (Auditory nerve Response Telemetry), ESRT (Electrically Evoked Stapedius Reflex Threshold), EABR (Evoked Auditory Brainstem Response) and Audiogram functions. The MAESTRO software is an external component of the MED-EL Cochlear Implant System and is intended to be used in a clinical or office environment by persons adequately skilled and trained to perform all intended tasks and with patients who received one of the intended MED-EL Cochlear implants.

For the pediatric population, the MED-EL Synchrony cochlear implant is currently indicated for children 12 months to 17 years and 11 months of age, who have bilateral sensorineural hearing impairment and obtain limited benefit from appropriately fitted binaural hearing aids. In this study, the use of this system is considered investigational because it will be used for children who have unilateral moderate to profound sensorineural hearing loss rather than bilateral profound sensorineural hearing loss.

5) Study Duration

- a) Enrollment Period
4 years

- b) Study Timeline

Each participant's involvement will last approximately 2.5 years, including: candidacy evaluation, preoperative evaluation, surgical procedure, initial activation of the external speech processor, therapy schedule, and post-initial activation evaluations (3, 6, 9, 12, 18 and 24-months post-initial activation).

- c) Study Endpoint

The study endpoint for each participant is the 24-months post-initial activation interval.

6) Methods

- a) All procedures will be conducted by UNC investigators, including board-certified otologists, audiologists, and speech-language pathologists. Fully informed consent will be obtained from all participants and/or their parents.
- b) Participants must meet the following inclusion criteria and not exhibit any of the exclusion criteria.
 - i) Inclusion Criteria
 - (1) Unilateral moderate-to-profound sensorineural hearing loss.
 - (a) Unaided residual hearing thresholds that yield a PTA at frequencies 500Hz, 1K Hz and 2K Hz of ≥ 70 dB HL in the ear to be implanted. It is possible that subjects may have hearing at other frequencies not included in this average.

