
- (3) Test materials to include:
 - (a) 3 subtests of Early Speech Perception Test (ESP), if > 70% then,
 - (b) CNC words
- iv) Speech Perception in Noise in binaural condition (6, 12, and 24 months post-initial activation)
 - (1) Speech processor on
 - (a) Listening conditions, noise orientation
 - (i) Speech and noise at 0° azimuth.
 - (ii) Speech 0° azimuth and noise to implanted side
 - (iii) Speech 0° azimuth and noise to contralateral ear
 - (b) Speech perception materials
 - (i) BKB-SIN
 - (2) Speech processor off
 - (a) Listening conditions, noise orientation
 - (i) Speech and noise at 0° azimuth.
 - (ii) Speech 0° azimuth and noise to implanted side
 - (iii) Speech 0° azimuth and noise to contralateral ear
 - (b) Speech perception materials
 - (i) BKB-SIN
- v) Sound Field Localization Measures (3, 9, 18, and 24 months post-initial activation)
 - (1) Postoperative aided sound field assessment will be measured in the free field with the Sonnet speech processor turned on and with the processor turned off.
 - (2) Testing will be completed in a double-walled soundproof booth. Eleven loudspeakers are arrayed in a 180-degree arc, with speakers evenly spaced at 18-degree intervals. Speakers are mounted at ear level, all spaced approximately 1-meter from the listener.
 - (3) The stimulus is a 200-ms speech-shaped noise, presented at 70-dB SPL. The speaker used to present the stimulus is randomly selected from the 11 alternatives on each trial, with the caveat that each speaker is used 3 times during a block of 33 trials. At least one block of 33 trials will be obtained in each condition (with and without the processor turned on).
 - (4) The listener faces the middle speaker prior to and during stimulus presentation. The task is to identify the source of the noise. Feedback is provided during instruction and training trials, but not during data collection.
 - (5) Listening Conditions
 - (a) Cochlear implant speech processor off at the 3, 9, 18 and 24 month intervals
 - (b) Cochlear implant speech processor on at the 3, 9, 18 and 24 month intervals

- (6) Performance is analyzed by computing the normalized RMS error, a metric that characterizes a listener's ability to discriminate between sound source locations.
- (7) These procedures have been used successfully to test children as young as 4 years of age.

vi) Parent questionnaires

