- b) A single-subject design will be utilized, where each participant serves as his or her own control, for analysis of objective and subjective results. A single-subject design was chosen in order to accommodate the heterogeneity that is well known to characterize auditory prosthesis research. Repeated-measures ANOVA will be calculated with a p-value of ≤ 0.05 for statistical significance. Statistical analysis will be conducted with SPSS software.
 - i) Comparison of aided speech perception performance to the baseline condition (either unaided or aided with hearing aid, depending on the participants residual hearing) and in the post-initial activation intervals to evaluate trends over time
 - ii) Comparison of localization abilities to the baseline condition (either unaided or aided with hearing aid, depending on the participant's residual hearing) and in the post-initial activation intervals to evaluate trends over time
 - iii) Compute the overall rms error, random error, constant error, and adjusted constant error, as described by Grantham et al (2007)
 - iv) Comparison of subjective report scores in the post-initial activation intervals. Group means compared with Bonferroni's adjusted t tests or repeated-measure ANOVAs. Pearson's correlations will be used to analyze relationships between variables.
 - v) Subjective report scores will be compared to norms for this test. Group means compared with Bonferroni's adjusted t tests or repeated-measure ANOVAs. Pearson's correlations will be used to analyze relationships between variables.
- c) The incidence of interference between ears will be assessed at the 6,12 and 24 month post initial stimulation visit by comparing the speech perception performance in the 0° azimuth conditions for the contralateral ear only versus cochlear implant + contralateral ear conditions for each participant, as well as the individual's subjective report.

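### Section 8.b tests trends over unequally spaced visits with a repeated-measures ANOVA that has no stated sphericity correction and does not use visit timing

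*Combined protocol and SAP*

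**What the plan says.** Section 8.b sets the test and its threshold: "Repeated-measures ANOVA will be calculated with a p-value of" 0.05 or less for significance. It adds that "Statistical analysis will be conducted with SPSS software". Items 8.b.i (speech perception) and 8.b.ii (localization) ask for a comparison with baseline and for a comparison "in the post-initial activation intervals to evaluate trends over time". For the questionnaires, 8.b.iv and 8.b.v leave a choice: "Group means compared with Bonferroni's adjusted t tests or repeated-measure ANOVAs".

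Section 8 does not mention sphericity, an epsilon correction, a covariance structure, a mixed model, polynomial contrasts or how visit time enters the analysis.

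The visits are unequally spaced:

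- **Speech in quiet and questionnaires:** section 5.b lists "post-initial activation evaluations (3, 6, 9, 12, 18 and 24-months post-initial activation", so the gaps are 3, 3, 3, 6 and 6 months. A preoperative point makes seven.
- **Speech in noise:** section 6.d.iv has "Speech Perception in Noise in binaural condition (6, 12, and 24 months post-initial activation", so the gaps are 6 and 12 months.
- **Localization:** section 6.d.v has "Sound Field Localization Measures (3, 9, 18, and 24 months post-initial activation", so the gaps are 6, 9 and 6 months.

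Section 8 plans for 20 children and allows for about 20% dropout.

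**The concern.** There are two separate problems.

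**Error rate.** The ordinary F test over three or more visits holds its level only under sphericity, meaning that the differences between any two visits all have the same variance. Equal variances with equal correlations are one case that satisfies this. It fails if neighbouring visits correlate more than distant ones, or if children progress at different rates. The plan itself gives reason to expect the second: 8.b justifies its design by the heterogeneity of outcomes in this field, and the sample-size paragraph refers to known variability among implant recipients. A result reported at 0.05 may then carry a larger false-positive rate.

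**Estimand.** The F test asks whether any visit mean differs from the others. It gives the same answer if the visits are shuffled or the calendar is changed. It therefore yields no rate of change and does not separate a plateau from continued gain, although 8.b.i and 8.b.ii ask about trends. The analyst would have to add something the plan does not specify.

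**Working it through.** **Inputs.** The threshold (0.05), visit months and sample size are from the plan. Completers: 20 × (1 − 0.20) = 16. The plan gives no effect size, SD or power behind the 20, so it has no derived figure to reproduce. The correlations are assumptions. The preoperative point is placed at month 0, also an assumption.

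**Mechanism.** With k visits and n children, the uncorrected test refers F to k − 1 and (k − 1)(n − 1) degrees of freedom. When sphericity fails, F behaves approximately as if both were multiplied by ε, where ε = (tr M)² / [(k − 1) tr(M²)] and M is the covariance matrix of k − 1 orthonormal contrasts. For k = 7 and n = 16 the nominal degrees of freedom are 6 and 90, with critical value 2.20. If the correlation is 0.95 per 3 months, ε = 0.43, so the effective values are 6 × 0.43 = 2.58 and 90 × 0.43 = 38.7. The chance of exceeding 2.20 is then about 11% by this approximation. Simulation gives about 10%.

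**Control.** Simulating equal correlation of 0.6 with n = 16 gave 4.8 to 5.0%, which recovers the nominal level.

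**Simulated error of the uncorrected test**, no true change, n = 16 or 20, correlation decaying at 0.5 to 0.95 per 3 months with no added visit noise:

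| Series | Points | Uncorrected error |
|---|---|---|
| Preoperative plus six visits | 7 | 6.2 to 10.3% |
| Six post-activation visits | 6 | 6.1 to 9.4% |
| Localization | 4 | 5.1 to 7.5% |
| Speech in noise | 3 | 5.0 to 6.3% |
| On versus off | 2 | 5.1% |

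**Adding independent visit noise** (n = 16, correlation 0.98 to 0.90 per month for the remainder). For six visits, the error falls to 5.9 to 6.5% when noise is 20% of the variance, and to 5.3 to 5.5% when it is 50%. At 20% noise, localization is 5.5 to 5.7% and speech in noise 5.2 to 5.3%.

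**Children differing in slope** instead of decaying correlation. The seven-point series gave 5.2 to 7.3% under one set of slope spreads; a further set gave 5.7 to 9.1%. These ranges depend on the spreads chosen and are not upper bounds.

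**After correction**, seven points, decaying correlation: Greenhouse-Geisser 3.5 to 4.7%, Huynh-Feldt 5.0 to 5.8%.

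**Spacing, if equal-step quadratic contrasts were added.** Apply each to the visit months themselves, which form an exact straight line, so the answer should be 0:

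- Six speech visits: 5(3) − 6 − 4(9) − 4(12) − 18 + 5(24) = 27.
- Speech in noise: 6 − 2(12) + 24 = 6.
- Localization: 3 − 9 − 18 + 24 = 0, because gaps of 6, 9, 6 are symmetric.

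The false quadratic part is 2.5 to 3.6% of the sum of squares for the speech and noise series. With n = 16 and assumed total growth of 1, 2 or 3 SD, a significant positive quadratic appears in about 9 to 13%, 24 to 38% and 46 to 70% of simulated trials. For localization it stays at about 2.5%, the nominal upper tail. Coding in actual months returns the other series to about 2.5%.

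**The case against.** **The plan does not commit to an uncorrected test.** It says only repeated-measures ANOVA, so this is under-specification. That is right. It still matters: if the software prints both corrected and uncorrected results, the plan does not say which one decides significance.

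**The upper error rates are a corner case.** Purely decaying correlation with no measurement noise is unfavourable to ANOVA. A 50-word list and blocks of 33 localization trials in young children must carry visit-to-visit noise. This stands, and it is why about 5 to 7% is the more realistic range and 9 to 10% the upper end.

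**The main claims are untouched.** Section 7 compares implant on with implant off, and section 9.b compares implant on with the preoperative condition. As two-level comparisons these need no sphericity. Questionnaire means may be compared with Bonferroni-adjusted t tests. This also stands.

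**A straight-line mixed model cannot show a plateau.** Correct, so the fix needs a curvature term or categorical visit where that question matters.

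**A stronger reading to resist.** A reader might infer that the plan will mistake steady growth for acceleration. The documents do not support this. The named F test does not use visit spacing at all. The distortion needs equal-step polynomial contrasts, which section 8 neither names nor excludes. Even then its frequency depends on growth and SD that the documents do not give, and the quadratic is exactly zero for localization.

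**Conclusion.** The point holds for the analyses over visits. As written, 8.b leaves the error rate of those tests uncontrolled if sphericity fails, and names a test that does not estimate the trend it is meant to assess.

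The excess error is modest under realistic noise: roughly 5 to 7% against a nominal 5%. It reaches about 9 to 10% only for the 6- or 7-point series with strong serial correlation and little noise, and is at most about 7.5% for localization and about 6% for speech in noise under the decaying correlations examined. These sizes rest on assumed correlation structures, so it would be too strong to say that the significance level is known to be 10%, or known to differ from 5%. False curvature is conditional on a contrast the plan does not specify, and applies to the speech and noise schedules only. The on/off comparison is not affected.

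**What to change.** Amend 8.b in one of two ways.

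1. **Preferred.** Analyse trends with a linear mixed model on actual months since activation. Include child random effects (a random slope where it can be fitted) and small-sample degrees of freedom. Add a curvature term, or use categorical visit, if plateau is of interest. This estimates the rate of change directly and keeps children who miss a visit, which classical repeated-measures ANOVA on complete series does not.
2. **Minimum.** Keep the ANOVA, state in advance that p comes from the Greenhouse-Geisser or the Huynh-Feldt correction, and code any trend contrasts in actual months: 3, 6, 9, 12, 18, 24 for speech in quiet; 3, 9, 18, 24 for localization; 6, 12, 24 for noise.

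Both need changes of wording only, with the same data. The price is slightly larger p-values. Greenhouse-Geisser is mildly conservative here (about 3 to 5%), and Huynh-Feldt can sit slightly above 5%. A random slope may not be estimable with three noise visits in about 16 children, so the plan should name the simpler model to fall back on.

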Appendix A graphically depicts the timeline and associated measures

i) **Candidacy Evaluation.** This interval may overlap with the Preoperative Evaluation interval.

- (1) Audiologic Evaluation
 - (a) Unaided air- and bone-conduction thresholds in both ears
 - (i) Air-conduction assessed with inserts
 - (b) Unaided word recognition in both ears
 - (i) Measured with recorded CNC words (50-word list)
 - (ii) Masking provided when appropriate (Turner, 2004)
 - (c) Tympanometry in both ears
 - (d) Aided word recognition in the affected ear
 - (i) Measured with recorded CNC words (50-word list)
 - (ii) Masking applied to the contralateral ear
 - (e) Completion of all questionnaires
 - (f) Determine if potential participant meets candidacy criteria
- (2) Speech-language and psycho-education evaluation
 - (a) Oral Written Language Scale (OWLS-II)
 - (b) Goldman Fristoe Test of Articulation
 - (c) Leiter-R
- (3) Medical Evaluation
 - (a) Determine if potential participant is healthy enough to undergo cochlear implantation
 - (b) Associated imaging studies
 - (c) Discussion of alternative treatment options
 - (d) Determine if potential participant meets candidacy criteria
- (4) Informed Consent
 - (a) Review and discussion of consent form
 - (b) Provide time for participant and/or parents to review consent form and ask questions
 - (c) Provide participant and/or parents with a signed copy of the completed consent form

The Preoperative Evaluation will be completed within 6 months of the surgery date.

- (1) Audiologic Evaluation
 - (a) Obtain a case history, including but not limited to:
 - (i) Onset of hearing loss
 - (ii) Stability or progression of sensorineural hearing loss
 - (iii) Suspected etiology of hearing loss

- (b) Unaided air- and bone-conduction thresholds in both ears assessed with insert phones
- (c) Unaided word recognition with CNC words in both ears
 - (i) Measured with recorded CNC words (50-word list)
 - (ii) Masking provided when appropriate (Turner, 2004)
- (d) Tympanometry in both ears
- (2) Speech-language and psycho-education evaluation
- (3) Parental Questionnaires – will serve as anchor point for future questionnaires
- (4) Counseling of parents on cochlear implant external technology, realistic expectations, study test battery, and postoperative timeline
- (5) Medical Evaluation
 - (a) Participants will undergo a medical assessment and review of medical history
 - (b) Associated imaging studies

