 - (i) This is standard of care for these patient populations
 - (ii) May have been completed at Candidacy Evaluation
 - (c) Counseling on cochlear implantation surgical procedure and postoperative considerations, including MRI limitations due to internal magnet

iii) **Surgery: Cochlear Implantation**

Risk factors associated with cochlear implantation are listed in Section XI “Risk Analysis.”

All surgical procedures will take place at the UNC Memorial Hospital or UNC Ambulatory Care Center (ACC) operating rooms. All procedures will be completed by board-certified otologists.

iv) **Postoperative Evaluations and Follow up Visits**

- (1) Initial Follow-Up (approximately 1-3 weeks postoperatively)
 - (a) Medical Evaluation
 - (i) This is standard of care
 - (ii) Participant will be seen by the physician
 - (b) Audiologic Evaluation
 - (i) Unaided thresholds
 1. Air-conduction assessed with an insert phone in the contralateral ear
 2. Bone-conduction thresholds assessed in the surgical ear
- (2) Initial Activation of External Speech Processor (approximately 2-4 weeks postoperatively)
 - (a) Initial activation of external speech processor

- (i) Participants will be fit with the commercially available MED-EL audio processor (MED-EL Corporation, Innsbruck, Austria).
Speech perception and localization measures at follow-up intervals will be conducted with the participant listening with the Sonnet external speech processor for the aided conditions
- (ii) Mapping will be completed by board-certified audiologists.
- (b) Counseling on the external device and use
- (c) Aural habilitation session

(3) Two-weeks Post-Initial Activation

- (a) Mapping of the external speech processor
- (b) Counseling on the external device and use as needed
- (c) Aural habilitation session

(4) Five-weeks Post-Initial Activation

- (a) Mapping of the external speech processor
- (b) Counseling on the external device and use as needed
- (c) Aural habilitation session

(5) Three-Months Post-Initial Activation

- (a) Localization assessment
- (b) Parental questionnaires – anchored to prior questionnaires
- (c) Speech perception assessed with the cochlear implant via direct input to processor
- (d) Mapping of the external speech processor

(6) Six-Months Post-Initial Activation

- (a) Hearing in noise assessment
- (b) Parental questionnaires - anchored to prior questionnaires
- (c) Speech perception assessed with the cochlear implant via direct input to processor

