A sample size of 20 participants was selected due to known variability in conventional cochlear implant recipient outcomes and to allow for possible dropouts (approximately 20%). A comparable study, Hansen, Gantz & Dunn (2013) evaluated 29 adult cochlear implant participants with UHL, which included etiologies of sudden sensorineural hearing loss, Meniere's disease, and vestibular schwannoma. Authors reported a high degree of variability in their sample. This project will not enroll all of the etiologies included in the Hansen, Gantz & Dunn (2013) analysis (such as, Meniere's Disease with intractable vertigo or history of vestibular schwannoma), therefore a smaller sample size was selected. The inclusion/exclusion criteria associated with this study, as compared to the heterogeneity of the Hansen, Gantz, & Dunn (2013) subject sample, will allow for more generalized comments about subjective and objective outcomes of cochlear implantation in pediatric cases of UHL.

If needed, statistical consultation will be sought from the North Carolina Translational and Clinical Sciences Institute (TraCS) or UNC Odum Institute.

9) Endpoints

- a) Safety endpoint
 - i) The primary safety endpoint is the evaluation of Adverse Events. All Adverse Events will be reported to the UNC IRB. If the UNC IRB or study investigators deem an Adverse Event unacceptable, then this would result in termination of the study.
- b) Primary effectiveness endpoint
 - i) The primary effectiveness endpoint is the comparison of speech perception, localization abilities and/or subjective report when the cochlear implant is on versus the preoperative unaided condition as well as changes in quality of life as measured by the Speech, Spatial and Qualities of Hearing Scale (SSQ), (Gatehouse & Noble 2004), the modified Bern SSD Questionnaire, (Kompis, Pfiffner, Krebs & Caversaccio , 2011) and the PedsQL Multidimensional fatigue scale (Varni, Limbers & Burwinkle, 2007).

10) Risk Analysis

- a) Potential risks to cochlear implantation

The following are risks associated with the MED-EL Synchrony implant, which is included in the device description:

1. Loss of residual hearing
2. Dizziness
3. Increased vertigo
4. Delay of healing of the scar
5. Impairment of the sense of taste

6. Potential for swallowing difficulties
7. Numbness
8. Increased tinnitus
9. Stimulation of the facial nerve
10. Temporary pain and uncomfortable sounds during stimulation

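### The questionnaire analysis in 8.b.iv names only post-activation visits, so no analysis item carries out the preoperative comparison that 9.b puts in the primary effectiveness endpoint

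*Combined protocol and SAP*

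**What the plan says.** Section 8.b (Statistical Analysis) opens with a single-subject design in which "each participant serves as his or her own control, for analysis of objective and subjective results", analysed by repeated-measures ANOVA at 0.05. The items below it differ by outcome:

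- 8.b.i, speech perception: "Comparison of aided speech perception performance to the baseline condition", and also across the post-activation visits for trends.
- 8.b.ii, localization: "Comparison of localization abilities to the baseline condition", with the same addition.
- 8.b.iv, questionnaires: "Comparison of subjective report scores in the post-initial activation intervals", using Bonferroni-adjusted t tests or repeated-measures ANOVA.
- 8.b.v, questionnaires: "Subjective report scores will be compared to norms for this test".

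Section 9.b lists speech perception, localization "and/or subjective report when the cochlear implant is on versus the preoperative unaided condition as well as changes in quality of life", the last of these measured by the SSQ, the modified Bern questionnaire and the PedsQL fatigue scale.

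In section 6.c, the preoperative questionnaires "will serve as anchor point for future questionnaires". Those at 3, 6, 9, 12, 18 and 24 months are described as "anchored to prior questionnaires".

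**The concern.** Items 8.b.i and 8.b.ii each have two parts: a comparison with baseline, and a look across the post-activation visits. Item 8.b.iv keeps the second and omits the first. With the parallel items directly above it, an analyst would naturally take 8.b.iv to concern post-activation visits only.

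A comparison among months 3 to 24 does not estimate what 9.b asks for. A benefit that has fully arrived by month 3 cancels out of every such contrast. A benefit that keeps growing is understated, because its first part is subtracted away.

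The comparator for subjective benefit also varies. It is the preoperative condition in 9.b, implant on versus off in 7.a.i, and either of these in 11.d. The visit lists in section 6.c schedule no processor-off questionnaire (the Appendix A timeline is not shown). The preoperative score is thus the only pre-implant reference visibly collected, and it is the one 8.b.iv leaves out. If the contrast is not named in advance, the comparator could be chosen after the data are seen.

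**Working it through.** **Text check.** No stated figure depends on this point, so there is none to reproduce. The remaining items of section 8 do not fill the gap: 8.b.iii concerns localization error, 8.b.v norms, and 8.c interference between ears. Six post-activation visits give 6×5/2 = 15 pairwise contrasts per score, none of which uses the preoperative score. Adding that score gives 7×6/2 = 21.

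**Illustration of size.** The plan supplies 20 children, about 20% dropout (20 × 0.80 = 16), six visits and alpha 0.05. It gives no effect size, SD, correlation or trajectory. The following are therefore assumptions:

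- One score, with correlation ρ = 0.5 between any two visits.
- A gain of 0.75 SD over the preoperative score at 24 months.
- A fraction p of that gain present at 3 months, then linear growth to 24 months. Steady growth from activation is p = 3/24 = 12.5%.

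Mean at month v, in SD units: m(v) = 0.75 × [p + (1 − p)(v − 3)/21]. The preoperative mean is 0.

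Repeated-measures ANOVA with k levels: noncentral F with λ = n × Σ(m − mean)² / (1 − ρ) and df k − 1 and (k − 1)(n − 1). This gives df 5 and 75 for the six post-activation visits, and 6 and 90 once the preoperative score is added.

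| p | Σ(m − mean)², 6 levels | λ | Rejects | Σ(m − mean)², 7 levels | λ | Rejects | Month 24 minus month 3 (SD) |
|---|---|---|---|---|---|---|---|
| 100% | 0 | 0 | 5% | 0.482 | 15.4 | 83% | 0 |
| 75% | 0.024 | 0.8 | 8% | 0.379 | 12.1 | 71% | 0.19 |
| 50% | 0.098 | 3.1 | 22% | 0.344 | 11.0 | 66% | 0.38 |
| 12.5% | 0.299 | 9.6 | 62% | 0.419 | 13.4 | 76% | 0.66 |

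For p = 50%, for example, λ = 16 × 0.0976/0.5 = 3.12.

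Over ρ from 0.3 to 0.7 and gains from 0.5 to 1.0 SD, the post-activation ANOVA rejects in 5%, 6–17%, 9–60% and 21–99% of trials in the four rows. With the preoperative level the ranges are 31–100%, 24–99.7%, 22–99.4% and 27–99.9%.

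A simulation in which the correlation falls from 0.75 at 3 months apart to 0.50 at 24 months apart, with Greenhouse-Geisser correction, gives about 4, 9, 24 and 66% against 90, 76, 68 and 75%. The pattern is the same.

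**A single paired contrast**, 24 months versus preoperative: SE = √(2(1 − 0.5)/16) = 0.25 SD, so the noncentrality is 0.75/0.25 = 3.0 on 15 df. Two-sided power is 80% at 0.05, 62% at 0.05/3 (three questionnaires), 51% at 0.05/6 (preoperative against each visit) and 31% at 0.05/21 (all pairs). The 95% confidence interval half-width is 2.131 × 0.25 = 0.53 SD (0.63 to 0.41 SD for ρ from 0.3 to 0.7).

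**The case against.** The strongest reply is that this is a wording gap in a combined document whose intent is plain. Section 9.b names the preoperative condition, the lead-in to 8.b extends the own-control design to subjective results, and section 6.c collects preoperative questionnaires as the anchor. Item 8.b.iv names no comparator and omits the trend wording of 8.b.i and 8.b.ii, so it could be saying when scores are compared rather than what they are compared with. The study is a feasibility study, and subjective report sits in an and/or list.

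Much of this stands. A reader might infer that the sponsor has dropped the preoperative comparison or cannot make it. The documents do not support that: the scores are collected and the intent is recoverable. What remains is that none of these passages specifies the contrast. The lead-in names no reference time, and an ANOVA over six post-activation visits would satisfy it. The anchoring wording is undefined and belongs to the visit schedule, where prior could mean the previous visit. The quality-of-life clause in 9.b follows the and/or list and is not covered by it.

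Three further inferences go too far:

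- **That power falls from 80% to 5%.** This sets an unadjusted paired t test against a five-df omnibus test. The like-for-like figures are the two ANOVA columns. Item 8.b.iv offers Bonferroni-adjusted t tests, so an added t test might not run at 0.05.
- **That the plan fixes 24 months as the main contrast.** Section 5.c makes 24 months each participant's study endpoint, but 9.b names no visit.
- **That 7.a.i and 11.d must yield to 9.b.** The three sections differ and need reconciling, but which comparator prevails is the sponsor's choice.

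**Conclusion.** The concern holds as a gap between endpoint and analysis that should be fixed. Section 9.b includes a preoperative questionnaire contrast in the primary effectiveness endpoint, and no item in section 8 carries it out. Taken in its most natural sense, 8.b.iv estimates a different quantity. That conclusion comes from the text alone and needs no assumed number.

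The size of the loss does rest on assumptions. It is large if benefit comes early and small if it grows steadily (62% against 76% in the illustration), and the documents do not say which to expect. Nothing is irrecoverably lost, since the preoperative scores are already scheduled.

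**What to change.** 1. **Reword 8.b.iv** on the model of 8.b.i and 8.b.ii: compare questionnaire scores with the preoperative (anchor) score, and across the post-activation visits to describe trends. Make the preoperative score the first level of the repeated-measures ANOVA, and report the preoperative contrast with a 95% confidence interval.
2. **Say which instruments this covers.** It suits the SSQ and PedsQL fatigue scale. Section 6.d.vi describes the Bern form as rating perceived benefit of a hearing technology, so include the modified form only if its preoperative administration yields an interpretable score.
3. **State which contrasts the Bonferroni adjustment covers.** As a suggestion, 24 months versus preoperative is a reasonable main contrast.
4. **Reconcile the subjective-benefit comparator** across 7.a.i, 9.b and 11.d, given that the visit lists schedule no processor-off questionnaire.

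The cost is a few words, with no new visits or data and no change to the 0.05 level. Any Bonferroni adjustment does lower the power of the paired contrast, as shown in the working, so the family should be chosen deliberately and kept small.
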